## STUDY INTERVENTIONS

### **Enhanced Skills Training in Affective and Interpersonal Regulation (ESTAIR) (Cloitre et al., 2019)**

ESTAIR will be offered according to the protocol (Cloitre et al., 2019) by an experienced psychotherapist appointed for the study and trained to its delivery. Treatment sessions will be conducted individually. ESTAIR will consist of up to 25 sessions organised in 4 modules of about 6 sessions each tackling the symptoms of PTSD and DSO symptoms. The first initial session is a formulation session to link present difficulties and traumatic life events, discuss current issues and concerns, and collaboratively agree on relevant treatment goals.

ESTAIR entails a flexible application of tools that match participants' specific needs. The PTSD module provides narrative exposure to the traumatic memories and targets re-experiencing, avoidance, and hyperarousal symptoms. The AD module focuses on identifying and labelling feelings, emotion management, distress tolerance, and acceptance of feelings and experiencing positive emotions. The NSC module focuses on how to stay in the present moment and combat dissociation; self-compassion and mindfulness skills; challenging thinking patterns and developing a balanced view of self. The DR module focuses on exploration and revision of maladaptive schemas; effective assertiveness; awareness of social context; and flexibility in interpersonal expectations and behaviours that are displayed in social interactions.

**Update Note:** During the training of the psychotherapist in the ESTAIR intervention, slight modifications to the treatment protocol were made.

1. Given the pilot nature of the present study, it was determined that the modules would be delivered in a sequential manner, starting with the AD module, the DR module, the NSC module, and then finishing with the PTSD module if necessary.
2. It was determined that the ESTAIR protocol still consists of up to 25 sessions, starting with the initial formulation session and ending with the final summary and

relapse-prevention session. However, the number of sessions per module were modified from up to 6 sessions per module, to up to 5, 6, 5 and 7 sessions for the AD, DR, NSC and PTSD modules, respectively.

3. Given the decision to offer modules sequentially (see point 1 above), session 25 (summary and relapse-prevention) was modified. In order to avoid repetition of the content of final session of the PTSD module (that summarizes the client's work in relation to PTSD symptoms) and session 25 (that summarizes the client's work across all ESTAIR modules), it was decided that for the purposes of the present pilot it would be more suitable to extend the time allotted for the final PTSD module session to incorporate additional content of session 25.

Defined completers will be those who have a valid post-treatment assessment using the ITQ at the end of every module and are diagnosis free. The ITQ will be administered at the end of every module and if the person is CPTSD diagnosis free then they will be offered a full post-treatment assessment. Subsequent input from Combat Stress following completion of trial will be offered as required and as per normal service standards.

**Update Note:** The ITQ will be administered at the end of every module to inform clinician's understanding of veteran difficulties. Participants will receive all four treatment modules, and dropping below CPTSD diagnosis on the ITQ at the end of a module will not serve as an indication to end treatment. Treatment will run include all four modules, unless strong clinical rationale to not do so.

**Update Note:** Treatment "defined completers" will be those who complete 80% of treatment sessions and have received at least 1 session per module. This definition was added ad-hoc, as it was noted that the protocol was lacking a "defined completer" definition and concerns were raised that the absence of such a definition would risk overattributing drop-outs/withdrawals to the treatment and would limit the opportunity to attribute such drop-outs to non-treatment related factors.

### ***Treatment Fidelity***

The ESTAIR intervention will be administered by an experienced psychologist who will be trained in ESTAIR delivery. The therapist will be supervised by TK for the duration of the study. A selection of treatment sessions will be video-taped and assessed for treatment integrity and fidelity.

**Update Note:** All treatment sessions will be video-taped. A total of 8 different tapes from 8 participants will be randomly selected to assess treatment integrity and fidelity. Treatment integrity and fidelity will be assessed according to the ESTAIR treatment fidelity checklist.

### **Treatment as Usual (TAU)**

At present there are no recommended treatments for CPTSD. TAU will normally consist of receiving a mental health assessment by either a psychiatrist or psychologist. Following this, a treatment package will be developed that could include elements of psychoeducation, symptom-management, and trauma-focused cognitive behaviour therapy. Details of TAU interventions delivered for all participants in the TAU will be recorded.

**Update Note:** TAU will consist of receiving a mental health assessment by a mental health professional.

## OUTCOME MEASURES

Outcomes are as follows: **(i)** Retention & data completion rates at weeks 25 weeks post-treatment and 12-week follow-up, on the primary outcome; International Trauma Questionnaire (Cloitre et al., 2018) and secondary outcomes: PHQ Depression (Kroenke et al., 2001), GAD Generalised Anxiety (Spitzer et al., 2006), AUDIT Substance Misuse (Saunders et al., 1993), and PHQ-15 Medically Unexplained Symptoms (Kroenke et al., 2002) **(ii)** 12-month recruitment rate; **(iii)** participant & clinical staff views on trial & intervention acceptability and suggested changes. Baseline information on demographics including age, gender, marital status etc., will be gathered to characterise the sample.

A range of assessments will be administered by the research assistant to test the acceptability of primary (PTSD and CPTSD) (i.e. ITQ) and secondary outcomes (depression, anxiety, alcohol use, and somatisation) (e.g. GHQ-12, AUDIT). Participants in both groups will be asked to complete these outcome measures at baseline, after 25-weeks post-treatment and then again after at a 12-week follow-up. The ITQ will be also completed by the ESTAIR group at the end of every module. In addition, data will be recorded on retention and DNA rate. The research assistant will be masked to group allocation to demonstrate to future funders this is achievable in a future trial.

**Note:** The ITQ will be completed by the therapist and participant at the end of every model. Due to feasibility concerns, the research assistant will not be masked to group allocation when collected measures at baseline, post-treatment, and follow-up. This is not expected to have any impact on outcomes as all primary and secondary outcome measures are self-report.

### Primary Outcome

The International Trauma Questionnaire (ITQ; Cloitre et al., 2018). Six items represent the three clusters of PTSD: Re-experiencing, Avoidance, and Sense of Threat. CPTSD includes PTSD as well as three clusters reflecting Disturbances in Self-Organisation (DSO); Affective Dysregulation (AD), Negative Self-Concept (NSC), and Disturbances in Relationships (DR), all captured by 16 items. The endorsement of symptoms is scored on a 5-point Likert scale ranging from 0 (not at all) to 4 (extremely), indicating how much a symptom has affected them in the past month. The Likert scores can be recoded into six binary variables that in turn demonstrate meeting criteria for ICD-11 PTSD or CPTSD based on scores greater than 2. A diagnosis of PTSD requires endorsing at least one symptom in each of its three clusters as well as functional impairment. A diagnosis of CPTSD requires PTSD and endorsement of at least one of the three DSO clusters plus functional impairment.

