## BACKGROUND AND RATIONALE

The 11th version of the *International Classification of Diseases* (ICD-11) (WHO, 2018), produced by the World Health Organization (WHO), includes two trauma-based disorders; PTSD and Complex PTSD. The description of PTSD in ICD-11 is simpler than that provided within the DSM-5. In contrast to the 20 symptoms spread across four symptom clusters in DSM-5, ICD-11 PTSD includes just six 'core' symptoms across three clusters, each of which is directly related to one's traumatic exposure: re-experiencing in the here and now (Re: 2 symptoms), avoidance (Av: 2 symptoms), and a sense of current threat (Th: 2 symptoms). Diagnosis of ICD-11 PTSD requires the presence of one symptom per cluster, plus evidence of functional impairment. CPTSD is a broader diagnosis that includes the core PTSD symptoms plus an additional set of symptoms that are collectively referred to as 'disturbances in self-organisation' (DSO). These symptoms are intended to capture pervasive psychological disturbances associated with traumatic exposure and are distributed across three clusters: affective (hyper-activation and hypo-activation) dysregulation (AD), negative self-concept (NSC), and disturbances in relationships (DR). A CPTSD diagnosis requires that the PTSD criteria be met in addition to endorsement of symptoms from each of the DSO clusters.

Evidence from clinical samples (Karatzias et al., 2017) as well as population-based samples (Karatzias et al., 2019) suggests that CPTSD is a more common condition than PTSD in the UK. Although comparisons between general populations and military populations are lacking, in a recently completed cohort study (n=178) of a veteran help-seeking population in Combat Stress, it was found that 56% met diagnostic criteria for CPTSD versus 14% who met criteria for PTSD (Murphy et al., 2020). Identifying effective interventions to treat veterans with CPTSD is therefore of paramount importance.

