## **STUDY POPULATION AND RECRUITMENT**

Combat Stress received approximately 3400 veteran referrals across the UK between April 2018/2019. Based on a recently completed cohort study, it is predicted that about 1,900 will meet criteria for CPTSD. As such, potential participants will be recruited and screened via Combat Stress.

Potential participants will be drawn from those referred to the Southern Treatment Combat Stress Treatment Centre (Leatherhead). They will have completed a mental health assessment as part of the referral and registered with Combat Stress for treatment. Potential participants will meet criteria for CPTSD, as indicated by the ITQ completed during their initial assessment. All new referrals are discussed at a weekly case management meeting to determine eligibility based on the inclusion and exclusion criteria below:

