### **Inclusion criteria**

- Adults (18 years or older) in the caseload of Combat Stress
- UK armed forces veteran
- Help-seeking for trauma related psychological distress
- Meets diagnostic criteria for CPTSD as measured by the ITQ
- Proficiency in English language
- Signed informed consent provided

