### **Recruitment**

When entering Combat Stress' clinical service, veterans are offered a formal assessment by a member of the multi-disciplinary team (MDT). As part of this process, they complete various psychometric measures of health including the International Trauma Questionnaire (ITQ). All cases are discussed at a weekly case management meeting. The research assistant will be embedded within the clinical team at Combat Stress' treatment centre in Leatherhead, Surrey to facilitate recruitment for this study. Veterans meeting criteria for CPTSD on the ITQ and deemed ready for therapy by the MDT will be approached to participate in the study.

The following procedure will be followed to recruit participants for the study:

1. The research assistant will attend the case management meeting to screen veterans for eligibility for the study.
2. If eligible, the research assistant will approach potential participants by letter and will be sent the patient information sheet and consent form. This invitation will be followed up by telephone call by the research assistant to discuss questions about the study and to discuss participants' willingness to participate. At this meeting, it will be emphasised that participation is voluntary.

**Note:** Due to the COVID-19 pandemic, the patient information sheet and consent form letter will be sent to potential participants via email, and they will later receive a printed copy by post.

3. If willing to participate, participants will be asked to attend a one to one or on-line meeting with the research assistant. At this meeting they will be asked again if they have any questions about the study, sign the consent form and complete pre-treatment measures. All forms can also be returned via mail. Following this, they will be randomised to one of the two groups (TAU or ESTAIR).
4. The research assistant will then inform Combat Stress of the outcome so participants in the TAU or who opted out can be offered the standard treatment.

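### The protocol's only written ITQ rule for CPTSD asks for one of three DSO clusters, while its own definition of the disorder asks for all three

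*Combined protocol and SAP*

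**What the plan says.** The Background and Rationale section sets out the ICD-11 definition on which the trial is built: "A CPTSD diagnosis requires that the PTSD criteria be met in addition to endorsement of symptoms from each of the DSO clusters".

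The Primary Outcome section explains how the ITQ yields a diagnosis. It claims to apply the same classification: "The Likert scores can be recoded into six binary variables that in turn demonstrate meeting criteria for ICD-11 PTSD or CPTSD". For PTSD it asks for every cluster: "A diagnosis of PTSD requires endorsing at least one symptom in each of its three clusters as well as functional impairment". For CPTSD it does not: "A diagnosis of CPTSD requires PTSD and endorsement of at least one of the three DSO clusters plus functional impairment".

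Eligibility depends on this diagnosis in three places:

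- Study Population and Recruitment: "Potential participants will meet criteria for CPTSD, as indicated by the ITQ completed during their initial assessment".
- Inclusion criteria: "Meets diagnostic criteria for CPTSD as measured by the ITQ".
- Recruitment: "Veterans meeting criteria for CPTSD on the ITQ and deemed ready for therapy by the MDT will be approached to participate in the study".

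None of the three gives a scoring algorithm. The protocol carries many update notes, but none corrects the CPTSD sentence.

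**The concern.** Both sections claim to describe ICD-11 CPTSD, and they describe different sets of people. Nothing suggests that a broader definition was intended. The rule that looks wrong is also the only one specific to the ITQ, and the ITQ decides who enters. The multidisciplinary team adds a judgement of readiness for therapy, but the text mentions no further check on the DSO clusters.

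If the rule is applied as written, three things are affected:

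- **Recruitment feasibility.** The pool counted as eligible is wider than the stated population, so a recruitment rate achieved in it does not answer the question for CPTSD as defined. The pilot is meant to inform a larger trial of the same design, so the error could carry over.
- **Acceptability.** The fourth research question in the Aims concerns people with CPTSD. ESTAIR has a separate module for each DSO cluster, and an update note says participants receive all four modules. Someone without one or two of the clusters would be judging modules aimed at symptoms they did not endorse.
- **Comparability.** The referral projection rests on a cohort figure of 56%. A sample selected by a looser rule may not match that cohort.

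**Working it through.** **Inputs**

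- The two CPTSD rules, from Background and Rationale and from Primary Outcome.
- Cohort of 178 help-seeking veterans, from Background and Rationale: "it was found that 56% met diagnostic criteria for CPTSD versus 14% who met criteria for PTSD".
- About 3,400 referrals UK-wide in a year, about 1,900 of them predicted to have CPTSD, from Study Population and Recruitment.
- Target sample of 60, from Sample size.

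**1. The plan's own projection.** 3,400 × 0.56 = 1,904, which agrees with the stated figure of about 1,900. The projection therefore uses the cohort's CPTSD rate.

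**2. Where the rules differ.** Take a person who meets the PTSD criteria with functional impairment. Three clusters, each endorsed or not, give 2³ = 8 patterns.

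| DSO clusters endorsed | Patterns | Primary Outcome rule | Background rule |
|---|---|---|---|
| None | 1 | not CPTSD | not CPTSD |
| One | 3 | CPTSD | not CPTSD |
| Two | 3 | CPTSD | not CPTSD |
| Three | 1 | CPTSD | CPTSD |

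The Primary Outcome rule accepts 7 patterns, the Background rule accepts 1, and they disagree on 6. This shows that the rules are not equivalent. It says nothing about how many people are affected, because the documents give no pattern frequencies.

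**3. How many people this could be.** Three assumptions are needed, none stated in the documents: the cohort was scored with the all-three rule, its 14% is PTSD without CPTSD, and the trial sample resembles the cohort. Let *f* be the share of the PTSD-only group that endorses one or two DSO clusters. Then

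non-case share = 14*f* / (56 + 14*f*).

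| *f* | Non-case share | Of 60 | UK-wide pool of 3,400 |
|---|---|---|---|
| 0 | 0% | 0 | 1,904 |
| 0.25 | 3.5/59.5 = 5.9% | 3.5 | 2,023 |
| 0.5 | 7/63 = 11.1% | 6.7 | 2,142 |
| 1 | 14/70 = 20.0% | 12 | 2,380 |

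**4. Precision of the upper figure.** In the cohort, 0.56 × 178 = 99.7 and 0.14 × 178 = 24.9, so about 25 of 125 PTSD-positive people, or 20%. The Wilson 95% interval is 13.9% to 27.9%, which is 8.4 to 16.7 of 60. The figure of 12 is thus a point estimate at *f* = 1, not a hard ceiling.

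**5. Effect on reaching 60.** The projection is UK-wide and recruitment is at one centre (Leatherhead). That centre's share of referrals is not given, so this cannot be computed.

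**The case against.** The strongest reply is that this is a wording slip with little consequence. The Primary Outcome section itself says CPTSD comprises PTSD as well as the three DSO clusters, and its PTSD sentence requires each cluster, so a phrase was probably dropped. The sentence sits under outcomes and is not labelled as the screening rule. Screening uses the ITQ from the clinical service's routine assessment, and nothing shows that the clinic scores it by this sentence. The analyses barely use the diagnosis: Phases 1 and 2 model ITQ scores, progression depends on recruitment and completeness of ITQ data, the sample size is pragmatic, and update notes removed loss of diagnosis both as a reason to end treatment and from the completer definition. Any dilution occurs before randomisation and should favour neither arm. The 0% to 20% range rests on unconfirmed assumptions.

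Most of this stands, and it limits the consequences. A slip is plausible, actual misenrolment is not shown, and the treatment comparison is not biased by this. It does not remove the contradiction. The sentence remains the only ITQ-specific rule behind the entry criterion, and a reader of the protocol cannot tell which population was studied. After entry, the diagnosis matters only for status at the end of each module and for any reported loss of diagnosis.

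**Conclusion.** The concern holds. The written ITQ rule contradicts the protocol's own definition of CPTSD and, if followed at screening, admits people who are not cases by that definition. The textual conflict is certain; whether anyone was wrongly enrolled is unknown.

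As an illustration, 0% to 20% of those admitted (0 to 12 of 60) would be non-cases, with sampling uncertainty around the upper figure. If the cited cohort was not scored with the all-three rule, the documents give no bound at all. The issue bears on who was recruited and whom the feasibility and acceptability findings describe, not on the between-arm comparison of ITQ scores. It needs correcting because it concerns the entry criterion and a correction is cheap.

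**What to change.** 1. Reconcile the CPTSD sentence in Primary Outcome with the Background: PTSD criteria met, symptoms endorsed in each of the three DSO clusters, and functional impairment. State how many symptoms each DSO cluster requires; the documents give that count only for the PTSD clusters.
2. State that this single algorithm applies at screening and at every later ITQ.
3. Ask the clinic which algorithm it used at screening, and document the answer.
4. Re-score enrolled participants from their baseline ITQ items and report, by arm, how many do not meet the reconciled rule. The baseline ITQ is completed after consent and may not be the same administration as the screening ITQ, so the report should say so.
5. Keep all randomised participants in the intention-to-treat analysis whatever the re-score shows.

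The cost is one sentence in the protocol, one query to the clinic and a re-score for up to 60 consented participants. No new data are collected, and no records of people who did not consent are needed. If the clinic has been using the broader rule, the eligible pool would shrink by 0% to 20% under the assumptions above (at most 476 of 2,380 UK-wide at the cohort's point estimates), and recruiting 60 could take longer.

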### Secondary Outcomes

#### **Depression**

Nine symptoms of depression are measured by the *Patient Health Questionnaire-9* (PHQ-9; Kroenke et al., 2001). Respondents indicate how often they have been bothered by each symptom over the last two weeks using a four-point Likert scale ranging from 0 (*Not at all*) to 3 (*Nearly every day*). Possible scores range from 0 to 27, with higher scores indicative of higher levels of depression. To identify participants likely to meet the criteria for depressive disorder, a cut-off score of 15 was used as it has been reported that this score produces specificity of .96. The psychometric properties of the PHQ-9 scores have been widely supported.

#### **Generalized Anxiety**

Symptoms of generalized anxiety are measured using the *Generalized Anxiety Disorder 7-item Scale* (GAD-7; Spitzer et al., 2006). Like the PHQ-9, respondents indicate how often they have been bothered by each symptom over the last two weeks on a four-point Likert scale (0 = *Not at all*, to 3 = *Nearly every day*). Possible scores range from 0 to 21, with higher scores indicative of higher levels of anxiety. The GAD-7 has been shown to be a reliable and valid measure in multiple studies.

### **Alcohol Use**

The presence of an Alcohol Use Disorder (AUD; Saunders et al., 1993) will be measured using the AUDIT-C, a brief self-report measure comprised of the first three questions of the *Alcohol Use Disorders Identification Test*. The clinical utility of the AUDIT-C has been demonstrated in multiple samples including the general population, military veterans, and hospitalised patients. Scores on the AUDIT-C range from 0-12, and based on a nationally representative sample of adults from the United States, scores  $\geq$  four effectively capture a DSM-5 diagnosis of AUD.

### **Somatic Symptoms**

Medically unexplained symptoms will be assessed using the *Patient health Questionnaire-15* (PHQ-15; Kroenke et al., 2002). The scale includes the most prevalent DSM-IV somatization disorder somatic symptoms. Participants are required to rate the severity of 13 symptoms as 0 (“not bothered at all”), 1 (“bothered a little”), or 2 (“bothered a lot”). Responses are coded as 0 (“not at all”), 1 (“several days”), or 2 (“more than half the days” or “nearly every day”) to produce total scores ranging from 0 to 30 and scores of  $\geq 5$ ,  $\geq 10$ ,  $\geq 15$  represent mild, moderate and severe levels of somatization. The reliability and validity of the PHQ-15 are acceptable.

**Update Note: Friends and Family Test (FFT).** The FFT was added as an additional secondary measure to help infer the acceptability of the ESTAIR intervention in comparison to TAU. The FFT is a single item asking participants to indicate ‘how likely is it that you would recommend our service to your GP, family and friends if they needed similar care?’. Responses are indicated on a 5 point-Likert scale ranging from 1 (‘Extremely unlikely’) to 5 (‘Extremely likely’). The FFT is standardly administered as an end-of-treatment measure at Combat Stress.

